### **6.5.3 Tertiary endpoints**

Tertiary outcomes will be analysed with statistical methods appropriate for the specific outcome. A large number of tertiary endpoints are being recorded within the trial, e.g. levels of tamoxifen metabolites, proteins, lipids and hormones in blood, breast tissue changes, genetic polymorphism in germline DNA, mammographic density and levels of side effects 6 months after tamoxifen cessation. Since this is the first study of its type, the associations of nearly every possible combination of primary, secondary, and tertiary endpoints are of interest. We therefore expect a number of tertiary analyses to be performed. In the list below, we briefly specify some obvious examples of such analyses:

1. The association of dose of tamoxifen to blood concentration of tamoxifen metabolites (e.g. endoxifen) by CYP2D6 polymorphism status (a woman can be classified as an excellent, intermediate, or poor

[figure not shown]

Figure 2: Schematic picture of what a plot of proportion responders vs proportion drop-outs by study arm may look like. The arm with the greatest distance to the diagonal line gives the best tradeoff between efficacy and drop-out level.

metaboliser of tamoxifen based on polymorphism patterns in CYP2D6 [5]) will be analysed in a linear regression model with tamoxifen dose, CYP2D6 polymorphism status, and age as independent variables.

2. The association of plasma concentrations of endoxifen with responder status will be analysed with logistic regression both within treatment groups and among treatments groups (treatment group will be handled as a random effect in the latter case).

## 6.6 Sample size

Since we have five intervention arms and since we do the primary analysis on a "per arm basis", we have five chances to show noninferiority of the primary endpoint and we therefore need to correct for multiple testing. Standard methods for correcting for multiple testing (according to the methods by Bonferroni or Holm) are too conservative in this context, since they

rely on an assumption of independence between the tests whereas the tests here are clearly correlated. We will instead use the resampling based step-down method suggested by Romano, Shaikh, and Wolf [6], which seamlessly handles correlated tests (see also Section 6.7). The correlation structure of the tests is unknown and we therefore assume that the multiplicativity leads to that the  $\alpha$  decreases from 0.05 to 0.03 in order to declare a significant results (correction by Bonferroni would lead to an  $\alpha$  of 0.01).

With 168 participants in each study arm, the lower limit of the observed one-sided 98.5% confidence limit for the difference will be expected to exceed the non-inferiority margin 16.7 percentage points with a 80% power, assuming that the expected difference in responders between two arms is 0 and the proportion responders in the 20 mg tamoxifen group is 50%. With an estimated 30% drop-out rate, 240 patients in each group need to be randomized.

The trial is powered for the primary analysis. However, we here also briefly investigate the power for showing *both* noninferiority with respect to the primary endpoint and superiority with respect to the secondary endpoint. With 240 participants randomized to each study arm, we have 79% power to show both noninferiority with respect to the primary endpoint and superiority with respect to the secondary endpoint assuming that the proportion of drop outs is reduced by two thirds (from 30% to 10%) and 67% power if the proportion of drop outs is reduced by 50% (from 30% to 15%). (For these calculations, we use the same assumptions about the correlation of the tests as for the analysis of primary endpoint.)

The computations are based on the following formula:

$$n = f(\alpha, \beta) \frac{\pi_s(100 - \pi_s) + \pi_e(100 - \pi_e)}{(\pi_s - \pi_e - d)^2},$$

where  $\pi_s$  and  $\pi_e$  are the true percent 'success' in the standard (20mg) and experimental treatment group respectively, and

$$f(\alpha, \beta) = [\Phi^{-1}(\alpha) + \Phi^{-1}(\beta)]^2,$$

and  $\Phi^{-1}$  is the cumulative distribution function of a standardised normal distribution.

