7.11.5 Method of assigning participants to treatment groups

Randomisation will be performed by a CMO (Galenica AB). The participants will be randomized in blocks in where the 6 arms are distributed evenly. The study participant emergency code envelopes are kept by a 24/7 service provider (Apoteket AB in Lund) during the whole study. Researchers do not have access to the randomisation list. This means that the study is triple blinded, i.e. neither study participant, Karma Study Centre, nor researchers know which medication product was used for each study participant.

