groups of women treated with placebo, 1, 2.5, 5, and 10 mg compared to the group of women treated with 20 mg tamoxifen. We will use Fisher's exact test with an  $p$ -value of less than 0.05 (corrected for multiple testing, see Section 6.7) as a threshold to declare statistical significance. The non-inferiority margin is defined to be 16.7 percentage points; that is, we define non-inferiority to mean that the fraction of responders is not less than one third of the treated individuals (50% minus 16.7% = 33.3%). The null hypothesis is thus that the proportion of responders in women treated with placebo, 1, 2.5, 5, and 10 mg is 16.7 percentage points less than those women treated with 20 mg tamoxifen (i.e. the fraction of responders is less than one third). For rejection of the null hypothesis, the lower end of the confidence interval needs to be higher than -16.7%. For this to hold, the point estimate of an intervention arm can not be more than 5 percentage points lower than the percent responders in the 20 mg arm.

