## 6.7 Adjustment for multiplicity, confounders, and heterogeneity

Since we have five treatment arms and therefore five comparisons, we will need to adjust for multiple testing. The treatment arms are correlated,

since they are defined by different doses of the same drug. Thus, standard adjustment for multiple testing using the methods by Bonferroni or Holm are too conservative. Instead, we will use the bootstrap based method suggested by Romano, Shaikh, and Wolf [6], which seamlessly handles correlated tests. The correlation structure of the tests is unknown and we therefore assume that the multiplicativity leads to that the  $\alpha$  decreases from 0.05 to 0.03 in order to declare a significant results (correction by Bonferroni would lead to an  $\alpha$  of 0.01).

We will perform subgroup analyses, where the subgroups are CYP2D6 polymorphism status (excellent, intermediate, poor metaboliser [5]). CYP2D6 polymorphism status will be handled as a categorical fixed effect variable. Other subgroups will likely be studied in non-prespecified analyses.

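### SAP 6.6 and 6.7 assume without derivation that alpha falls from 0.05 to 0.03 and state neither its side nor the error rate; with 168 evaluable per arm, per-dose power is 71–76% at family-wise one-sided 0.025 and 80–85% at 0.05

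*SAP*

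**What the plan says.** SAP 6.6 gives the reason for adjusting: "we have five chances to show noninferiority of the primary endpoint". It rejects Bonferroni and Holm because they "rely on an assumption of independence between the tests whereas the tests here are clearly correlated", and SAP 6.7 explains the correlation between arms thus: "since they are defined by different doses of the same drug". Both sections then set the planning level by assumption: "The correlation structure of the tests is unknown and we therefore assume that the multiplicativity leads to that the" alpha goes from 0.05 to 0.03, with 0.01 quoted as the Bonferroni figure. The method to be applied is the resampling step-down procedure of reference [6], whose title names the false discovery rate.

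SAP 6.6 and protocol 10.6.3 size the trial with a one-sided 98.5% limit, a margin of 16.7 points and 50% responders in both arms. This gives 168 evaluable per arm for 80% power, and 240 randomised at 30% drop-out.

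SAP 6.3 declares significance at a p-value "of less than 0.05 (corrected for multiple testing, see Section 6.7) as a threshold to declare statistical significance". It adds: "For rejection of the null hypothesis, the lower end of the confidence interval needs to be higher than -16.7" percent, with no confidence level, and draws this consequence, with 20 mg as the reference: "the point estimate of an intervention arm can not be more than 5 percentage points lower than the percent responders". SAP 6.8 and protocol 10.6.7 quote 73% power at best for a drop-out level that is missing from the sentence.

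**The concern.** The level used for planning is assumed, not derived from the design, and the grounds offered for it are not the right ones. The text also leaves open what the primary analysis guarantees. The worry about five chances is a family-wise one, whereas the cited method by its title controls the false discovery rate. The 0.05 has no stated side.

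The primary objective is to name the lowest non-inferior dose, which the protocol's introduction intends to carry into Karisma III with 8,000 women. A reader should be able to say what error rate a dose claim was held to and what power stood behind it. As written, the 80%, the 5 points and the 73% all rest on the assumed 0.03.

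**Working it through.** **Inputs.** From SAP 6.6: 168 evaluable per arm, margin 16.7 points, 50% v 50%, one-sided 98.5% limit, five tests against one 20 mg arm. From protocol 7.11.5, on allocation: "The participants will be randomized in blocks in where the 6 arms are distributed evenly".

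**1. The plan's own figure.** With the SAP's formula at one-sided 0.015 (z = 2.170) and 80% power (0.842):

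n = (2.170 + 0.842)² × (50×50 + 50×50) / 16.7² = 162.6, so 163.

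The plan has 168, at which power is 81.4%. Other one-sided levels fit worse: 0.05 gives 111, 0.03 gives 133, 0.025 gives 141 and 0.01 gives 180. So the SAP halved 0.03, which implies that the 0.05 it started from is two-sided, that is, one-sided 0.025. This is an inference; the text does not say so. Also 168/0.7 = 240 and 240 × 6 = 1,440.

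**2. The correlation.** Each arm is a separate group of women, and all five differences share the 20 mg arm. The correlation of two differences is (1/n₂₀) / (1/n₂₀ + 1/n_dose), which is 0.5 with equal numbers. With 168 in the 20 mg arm and 204 in a lower-dose arm it is 204/372 = 0.548; with 216 it is 216/384 = 0.5625. A simulation that used the 20 mg sample median as the response threshold gave 0.48. The doses being of one drug plays no part. Bonferroni and Holm are valid under any dependence.

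**3. Critical values at correlation 0.5** (numerical integration). SE = √(0.5/168) = 5.455 points. Allowed shortfall = 16.7 − c × 5.455.

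| Tests remaining | 5 | 4 | 3 | 2 | 1 |
|---|---|---|---|---|---|
| c, family-wise one-sided 0.025 | 2.5115 | 2.4418 | 2.3490 | 2.2121 | 1.9600 |
| Shortfall (points) | 3.0 | 3.4 | 3.9 | 4.6 | 6.0 |
| c, family-wise one-sided 0.05 | 2.2338 | 2.1603 | 2.0621 | 1.9163 | 1.6449 |
| Shortfall (points) | 4.5 | 4.9 | 5.5 | 6.2 | 7.7 |

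At family-wise 0.025 the first-step level is 0.0060 one-sided, or 0.0120 two-sided: close to Bonferroni's 0.010 and well below 0.03. To allow 0.03 the correlation would have to be about 0.96.

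**4. Power at 168.** Margin/SE = 16.7/5.455 = 3.061. First-step power is Φ(3.061 − c): Φ(0.550) = 70.9% at 0.025 and Φ(0.827) = 79.6% at 0.05. Step-down per-dose power was simulated (200,000 draws) with the remaining arms clearly inferior:

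| Doses truly equal to 20 mg | 1 | 2 | 3 | 4 |
|---|---|---|---|---|
| Family-wise one-sided 0.025 | 71.0% | 72.3% | 74.1% | 76.3% |
| Family-wise one-sided 0.05 | 79.5% | 81.0% | 82.6% | 84.7% |

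If a false discovery rate were the target, Benjamini–Hochberg as an illustration gives 68–81% (0.025) and 77–88% (0.05).

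**5. The 5 points.** A fixed 98.5% limit allows 16.7 − 2.170 × 5.455 = 4.9 points. That is the SAP's figure. A step-down test has a different limit at each step, as the first table shows.

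**6. The 73%.** The plan's own pairing of 168 with 80% implies z = 3.061 − 0.842 = 2.22. At 40% drop-out, 240 × 0.6 = 144 evaluable, SE = √(0.5/144) = 5.893 points and margin/SE = 2.834. Power is then Φ(2.834 − 2.22) = 73%, so 40% is a plausible value for the missing drop-out level. At 144 the first-step power is Φ(2.834 − 2.5115) = 63% at 0.025 and Φ(2.834 − 2.2338) = 73% at 0.05.

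**The case against.** The 0.03 is only a planning stand-in, because the final test is to be bootstrap-adjusted. That stands, and it limits the point. A reader might infer that the planned analysis has a family-wise error of 5–6% instead of 2.5%. Five fixed 98.5% limits with all five arms exactly on the margin would give 5.8%, but SAP 6.3 and 6.7 do not plan to make claims that way, so this is not a property of the planned test.

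A reader might also infer that the trial is simply underpowered. The documents do not support that, for two reasons. The one-sided 0.025 start is inferred from the 98.5% limit, and at family-wise one-sided 0.05 the 80% is met. Also, 168 is a planning floor. Protocol 7.2 asks women who stop after a week or more to attend an exit mammogram, and SAP 6.1 and 6.9 include any woman with an eligible post-baseline measure, using last observation carried forward. At one-sided 0.025 first-step power reaches 80% at about 202 per arm, that is, if 202 − 168 = 34 of the 240 − 168 = 72 expected drop-outs per arm supply one. Attendance is voluntary, so the number is unknown.

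It would be too strong to say that no level is given: 0.05 is stated, and 0.01 is 0.05/5. Only the side and the type of error rate are missing. The SAP is also right that Bonferroni is slightly conservative here (0.010 against 0.012), though not for the reason it gives. Finally, the joint powers of 79% and 67% in SAP 6.6 are a brief side calculation that errs low and on which no decision rests; they need not be reworked.

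**Conclusion.** The point holds and should be fixed. The fall from 0.05 to 0.03 has no derivation and its stated grounds are wrong. The side of the 0.05 and the error rate are missing, and the cited method does not match the stated family-wise concern.

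The size depends on the reading. At family-wise one-sided 0.025, which the plan's own 98.5% limit implies, per-dose power is 71–76% instead of 80%. At family-wise one-sided 0.05 it is 80–85% and the stated figure stands. Both ranges assume 168 evaluable in every arm, a true difference of zero, correlation 0.5 and one to four doses truly equal to 20 mg. More evaluable women would raise both. The 5 points in SAP 6.3 do not describe the planned step-down test on either reading.

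**What to change.** - **SAP 6.7:** state the error rate, its level and its side. One option is family-wise one-sided 0.025 by a step-down max-T bootstrap that re-estimates the 20 mg median in each resample. If one-sided 0.05 or a false discovery rate is intended, say so and justify it.
- **SAP 6.6 and 6.7:** delete the 0.03 assumption and the arguments from independence and from the doses being of one drug.
- **SAP 6.6 and protocol 10.6.3:** restate power for 168 evaluable at the chosen level, 71–76% at family-wise one-sided 0.025 or 80–85% at 0.05. Keep 168 and 240.
- **SAP 6.3:** delete the 5 points, or give the step-specific limits (3.0, 3.4, 3.9, 4.6 and 6.0 points at one-sided 0.025).
- **SAP 6.8 and protocol 10.6.7:** supply the missing drop-out level and recompute the 73% at the chosen level for that evaluable number.

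The cost is text edits only, with no added participants, visits or data. Protocol 10.6 has the SAP finalised before database lock, so this can be done in the normal course. If one-sided 0.025 is chosen, the stated power becomes less favourable.

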10.6.3 Sample size

With 168 patients in each treatment group, the lower limit of the observed one-sided 98.5% confidence limit for the difference will be expected to exceed the non-inferiority margin 16.7 percentage points with a 80% power, assuming that the expected difference in responders between two arms is 0 and the proportion responders in the 20 mg tamoxifen group is 50%. With an estimated 30% drop-out rate, 240 patients in each group need to be randomized. The computations are based on the following formula:

$$n = f(\alpha, \beta) \times [\pi_s \times (100 - \pi_s) + \pi_e \times (100 - \pi_e)] / (\pi_s - \pi_e - d)^2$$

where π_s and π_e are the true percent 'success' in the standard (20mg) and experimental treatment group respectively, and

$$f(\alpha, \beta) = [\Phi^{-1}(\alpha) + \Phi^{-1}(\beta)]^2$$

 Φ^{-1} is the cumulative distribution function of a standardised normal deviate.

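### The 67% joint power in SAP 6.6 does not follow from 240 randomised per arm; the SAP's own inputs give about 76%

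*SAP*

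**What the plan says.** SAP 6.6 first sizes the trial for the primary analysis: 168 evaluable women per arm for 80% power, a margin of 16.7 percentage points, 50% responders in both arms, and a decision based on "the lower limit of the observed one-sided 98.5% confidence limit for the difference". Protocol 10.6.3 gives the same number ("With 168 patients in each treatment group"). Both documents then allow for 30% drop-out and arrive at 240 randomised per arm.

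SAP 6.6 next turns to a joint aim, non-inferiority on responders together with superiority on drop-out: "With 240 participants randomized to each study arm, we have 79% power to show both noninferiority with respect to the primary endpoint" and superiority on the secondary endpoint, if "the proportion of drop outs is reduced by two thirds (from 30% to 10" per cent). For the smaller reduction it gives "67% power if the proportion of drop outs is reduced by 50% (from 30% to 15" per cent).

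On alpha, the SAP assumes that multiplicity adjustment means it "decreases from 0.05 to 0.03 in order to declare a significant results", and it carries this over to the joint figures: "For these calculations, we use the same assumptions about the correlation of the tests as for the analysis of primary endpoint". SAP 6.4 and Protocol 10.6.4 both name Fisher's exact test for comparing drop-out with the 20 mg arm. The working behind the two joint figures is not shown.

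**The concern.** Drop-out is a proportion of all randomised women, so its test has 240 per arm, as the sentence itself says. A fall from 30% to 15% is large for that number, and the drop-out test should then rarely fail. If so, joint power should sit only a little below the 80% for non-inferiority alone. A printed value 13 points below 80% needs a drop-out power of only 0.67 / 0.80 = 84%, which looks too low for 240 per arm.

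This sentence is the only stated power for meeting both aims, and SAP 6.5.2 plans an analysis that looks at response and drop-out together. As printed, a reader would put the chance of missing at least one of the two aims at one in three in the 15% scenario. The stated inputs put it at just under one in four.

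**Working it through.** **Inputs**
- Randomised per arm: 240 (SAP 6.6).
- Drop-out: 30% in the 20 mg arm against 10% or 15% (SAP 6.6).
- Drop-out test: Fisher's exact test (SAP 6.4).
- Alpha: 0.03, taken as two-sided. This matches the one-sided 98.5% limit used for non-inferiority (0.015 per side).
- Non-inferiority power: 80% (SAP 6.6).
- Assumption made here, not stated in the SAP: the two test results are independent, so joint power = non-inferiority power × drop-out power.

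**Step 1: the primary sample size.** Using the printed formula,

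n = (2.170 + 0.842)² × (50×50 + 50×50) / 16.7² = 162.6.

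At 168 per arm the power is 81.4%, so the stated 80% is met with a little to spare. 168 / 0.7 = 240. These figures stand.

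**Step 2: trying to reproduce the joint figures.** Exact Fisher power at alpha 0.03, times 0.80:

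| Women per arm in the drop-out test | Drop-out | Fisher power | Joint power | SAP states |
|---|---|---|---|---|
| 240 | 30% v 10% | 0.9996 | 80.0% | 79% |
| 240 | 30% v 15% | 0.9563 | 76.5% | 67% |
| 168 | 30% v 10% | 0.9925 | 79.4% | 79% |
| 168 | 30% v 15% | 0.8485 | 67.9% | 67% |

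At 240 the first scenario agrees to about one point. The second is 76.5 − 67 = 9.5 points away from the printed value.

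**Step 3: whether another reasonable assumption gives 67% at 240 (30% v 15%).**
- Test approximation: a continuity-corrected normal calculation gives 0.954 × 0.80 = 76.3%; the pooled one gives 0.964 × 0.80 = 77.1%.
- Dependence: the smallest joint power under any dependence is 0.80 + 0.9563 − 1 = 75.6%.
- Stricter alpha: 0.015 gives 0.926 × 0.80 = 74.1%. Full Bonferroni at 0.01, which the SAP rejects as too conservative, gives 0.902 × 0.80 = 72.2%. At 0.005 the result is still 68.5%; 67% needs an alpha between 0.003 and 0.005, far below anything in the documents.
- Non-inferiority power of 81.4% instead of 80%: 0.814 × 0.9563 = 77.8%, further from 67%.

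**Step 4: what does come close.** Testing drop-out on 168 per arm gives 67.9% by exact Fisher and 67.5% with the continuity-corrected approximation (0.843 × 0.80), and 79.4% or 79.3% in the other scenario. Of the sample sizes named in SAP 6.6, 168 is the one that comes near both printed figures.

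**The case against.** The strongest reply is that little depends on this sentence. SAP 6.6 says the trial is powered for the primary analysis and looks at joint power only briefly. No sample size, decision rule or test rests on it, and the error understates power. All of that stands, and it keeps the point minor.

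The corrected value is also conditional. The SAP calls the correlation of the tests unknown, and 0.03 is its own assumption. This stands too, but every variation in the working leaves the result well above 67%.

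The cause is not established. The working is not shown, and the match at 168 is imperfect: exact Fisher gives 67.9%, which rounds to 68%. With 81.4% non-inferiority power the two figures at 168 become about 81% and 69%, and neither matches what is printed. Use of 168 is therefore a plausible inference and no more.

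A reader might infer three stronger things that the documents do not support:
- **That 168 per arm is also wrong, because the formula gives 163.** 168 meets its stated 80% power and is slightly conservative, so there is nothing to correct.
- **That the power figures in general fail.** The 79% is within about one point of 80.0%; only the 67% fails materially.
- **That joint power should be 86% and 81%, using 216 or 204 evaluable women in the low-drop-out arm.** This treats every drop-out as lost to the primary analysis. SAP 6.9 carries the last observation forward, and Protocol 7.2 asks women who stop after a week or more to attend an exit mammogram, so those counts do not follow from the plan.

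**Conclusion.** The 67% is wrong as written. With 240 randomised per arm, Fisher's exact test, alpha 0.03 two-sided, 80% non-inferiority power and independent results, joint power for 30% against 15% drop-out is about 76%, so the SAP understates it by about 9 points. At that alpha it cannot be below 75.6% under any dependence; with alpha at 0.015 and independence it is about 74%. The near match at 168 suggests that the number left after drop-out was used where the randomised number belongs, but the documents do not prove it. The consequence is small: a supplementary power statement is too pessimistic, and nothing in the design or analysis changes.

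**What to change.** In SAP 6.6, restate the joint power at 240 randomised per arm as about 76% for drop-out of 30% against 15%, and about 80% for 30% against 10%. Add one sentence giving the denominator for the drop-out test (all randomised women), the alpha and its sidedness, the non-inferiority power used, and the assumption that the two results are independent. If the authors used other inputs to reach 67%, they should state them in place of this correction. The cost is an edit to the SAP text; Protocol 10.6.3 does not carry the joint figures and needs no change.
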